## 9.4 Malnutrition

Participants identified as malnourished according to the clinical judgment of the loR/designee will be counseled regarding locally available treatment options and sources for nutrition support.

## 9.5 Clinical Management of Pregnancy

Participants who become pregnant will discontinue DXA scans and collection and storage of urine and serum, but will resume these procedures per their original substudy follow-up schedule after completion of the pregnancy.

# **10 STATISTICAL CONSIDERATIONS**

## 10.1 Overview and Summary of Design

This is a substudy conducted in an ancillary fashion to VOICE. All eligible participants randomized to oral study product will be enrolled at selected substudy sites. Follow-up assessments will occur semiannually throughout participation; follow-up assessments will also be completed at the VOICE PUEV or the BMD Substudy ETV if at least 30 days have passed since the last BMD Substudy semiannual follow-up visit.

## 10.2 Study Endpoints

## Primary endpoints

Consistent with the substudy objective to explore changes in BMD among VOICE participants using oral study products, the following primary endpoints will be assessed:

• Total hip and lumbar spine bone density via DXA

Note that these endpoints will be used also for the secondary objective to explore changes in BMD among VOICE participants using oral study products after discontinuation of product use.

Consistent with the substudy secondary objective to describe changes over time in nutritional status among VOICE participants receiving oral study products, the following secondary endpoints will be assessed:

• Nutritional assessment components, including height, weight, BMI, clinical findings, and dietary history

# **10.3 Primary Study Hypotheses**

## Primary endpoints

The protocol team hypothesizes that oral TDF and FTC/TDF will not cause a clinically significant decrease in BMD in substudy participants. Therefore, the null hypothesis is that there will be no difference in the safety profile between daily regimens of oral active products and oral placebo after one year of product use.

## **10.4 Sample Size and Power Calculations**

For the VOICE Study population, the estimated range of baseline means for single measurements of total hip and lumbar spine BMD at a given time point are between 1.0 and 1.2 g/cm^2 with standard deviation (SD) between 0.1 and 0.2 g/cm^2. Longitudinal measurements of BMD are highly correlated when correlation coefficients are in the range of 0.85 to 0.95, which translates to SD estimates in the range of 3.5% and 5.5% for the percentage change in BMD from baseline to a time point 12 months after initiation of follow-up. Through 144 weeks in Gilead Study 903, for example, the observed SDs for the percentage change in BMD from baseline for hip and lumbar spine was between 3.5% and 4.6%. Therefore, for sample size calculations in this substudy, we will assume that the SD for the percentage change in BMD from baseline to a time point 12 months after initiation of follow-up that the SD for the percentage change in BMD from baseline to a time point 12 months after spine was between 3.5% and 4.6%. Therefore, for sample size calculations in this substudy, we will assume that the SD for the percentage change in BMD from baseline to a time point 12 months after initiation of follow-up for the hip and lumbar spine is 4.5%. Duplicate measurements will be made at each time point since the variability associated with the instrument/operator is relatively high in comparison to between-subject variability.

For the purpose of sample size determination, we are conservatively assuming that a minimum of 300 women will be enrolled in the study (i.e. 100 women per oral arm). Given that at the selected sites all women enrolled into oral arms will be asked to participate in this study, the total enrollment will be between 300 and 540 women.

At each assessment time point during the expected product use period, the arithmetic mean of the duplicate measurements will be used for the following primary analysis. Two Student t-tests (two-sided) will be used to compare the percentage reduction in BMD between the TDF active arm, FTC/TDF active arm, and placebo arm. Analyses for hip and lumbar spine measurements will be done separately. Based on the above SD estimates, a sample size of 100 women per oral arm allows the detection of a difference as small as 2.1% with 90% power with a type one error rate of 5%. Note that this is a conservative estimate of power since the duplication of measurements at each time point will reduce the SD and thus provide power to detect lower differences (i.e., <2.1%). However, the reduction in SD is difficult to quantify since no data are currently available on the measurement error that could be anticipated at each of the proposed sites.

Similarly, the percentage change in BMD between the TDF active arm, FTC/TDF active arm, and placebo arm observed during the year after product use was discontinued will be compared. Based on similar assumptions as above, 100 women per oral arms will allow the detection of a difference as small as 2.1% with 90% power with a type one error rate of 5%.

## 10.5 Data and Safety Monitoring and Analysis

When the use of descriptive statistics to assess group or site characteristics or differences is required, the following methods will be used: for categorical variables, the number and percent in each category; for continuous variables, the mean, median, standard deviation, quartiles and range (minimum, maximum). To assess the differences between the three oral arms, participants will be compared for baseline characteristics including demographics using descriptive statistics.

For the primary analysis, two Student t-tests will be used to compare the percentage reduction after one year of follow-up in BMD between each of the following: (1) the TDF active arm and placebo oral arm; and, (2) FTC/TDF active arm and placebo oral arm. Analysis for hip and lumbar spine measurements will be done separately.

BMD hip and lumbar assessments are done every 6 months, but a substantial number of women will have terminated the VOICE trial before reaching their year-2 BMD assessments. Assuming uniform recruitment over 21 months, about 130 of the 300 women will have a year-2 BMD assessment. This reduction in participant numbers will result in a reduction of the statistical power in comparison to that observed following year-1. However, to explore possible trends over the entire follow-up time, GEE models for repeated measures will be used where BMD from all time points are included in the analysis. Similar methods will be used to compare changes after one/two year(s) of follow-up in bone turnover, bone mineral metabolism, and nutritional assessment components. Distribution of some of these endpoints may not allow the use of the Student t-test (e.g., height is expected to have very little variation over a year), in which case a McNemar's test approach might be used, or the proportion of women with an observed percentage change might be compared across arms using a Fisher exact test.

For evaluating changes in BMD after product use was discontinued, two Student t-tests will be used to compare the percentage change over the year of follow-up without product use in BMD between each of the following: (1) the TDF active arm and placebo oral arm; and, (2) FTC/TDF active arm and placebo oral arm. Analysis for hip and lumbar spine measurements will be done separately. Note that this analysis is more relevant in the case where at least one effect from the use the active oral products on BMD is observed. In that case, it would be worthwhile to investigate if the effect on the BMD is waning after product use is discontinued and eventually returns to its baseline values (i.e. prior to initiation of product use).

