# 2 INTRODUCTION

## 2.1 Vaginal and Oral Interventions to Control the Epidemic (VOICE)

The VOICE Study will simultaneously assess the safety and efficacy of daily dose oral and vaginal formulations of tenofovir (TDF) and oral FTC/TDF in preventing HIV acquisition. The study design of VOICE also allows limited comparisons of effectiveness, safety, adherence, and associated frequency of viral resistance among HIV seroconverters across formulations.

VOICE is a Phase 2B, five-arm, multi-site, randomized, placebo-controlled trial that is double-blinded within each mode of administration, but open-label with respect to the randomly assigned mode of administration (vaginal or oral). Approximately 5000 participants will be randomized to the five study arms in a 1:1:1:1:1 ratio.

While investigators and participants will be aware of randomization to either the oral or vaginal administration of study product, they will be blinded to the specific study products randomly assigned. All participants will complete monthly follow-up visits for a period of 12 to 36 months, and will receive ongoing HIV risk reduction counseling, condoms, and diagnosis and treatment of sexually transmitted infections (STIs) throughout the course of study participation. Participants will also be scheduled for a Termination Visit approximately 8 weeks following completion of their scheduled end-of-study product use.

The BMD Substudy will explore the potential effects of oral study products on BMD in a subset of VOICE participants.

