## 2.2 BMD Considerations in VOICE

## 2.2.1 Expected BMD of VOICE Participants

Based on the cross-sectional study of steroidal hormonal contraception and BMD by Petitti et al.—a study that included the UZ-UCSF site participating in the VOICE Study—it is expected that the baseline BMD of VOICE Study participants will be normal, if not higher than average. This study, conducted among women 30 to 34 years of age who were attending family planning clinics in Brazil, China, Egypt, Mexico, Thailand, and Zimbabwe from 1994-1997, indicated that mean BMD (g/cm^2) values ranged from 0.488 at the midshaft ulna and 0.409 at the distal radius in African women to an average of

0.462 at the midshaft ulna and 0.360 at the distal radius in Asian women (values adjusted for study site, age, BMI, years of lactation, years since last lactation stopped, and occupation of partner, except entry itself and colinear variables).

The possible contributory effect of two other modifiers on BMD also requires attention. First, some data indicate a small decrease in BMD from the use of the hormonal contraceptive, depot medroxyprogesterone acetate (DMPA). The difference in BMD among the DMPA users was less than one SD of the mean of the group who never used hormonal contraceptives. In the study by Petitti et al., use of DMPA was associated with a significantly lower adjusted mean BMD at the distal radius as measured by single x-ray absorptiometry. The BMD (g/cm^2) values among women in the DMPA group in the Petitti et al. study, measured 0.465 at the midshaft ulna and 0.369 at the distal radius (adjusted for study site, age, BMI, years of lactation, years since last lactation stopped, and occupation of partner, except entry itself and colinear variables), which is still higher than the BMD values for Asian women. Thus, the observed natural differences between different populations (African versus Asian) were apparently much greater than the differences due to contraceptive method used. It is important to note that data from the HPTN 035 study indicate that approximately 48% of study participants used DMPA and a similar proportion might be expected in the VOICE Study.

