# 2.2.2 Tenofovir

All three active study products in VOICE contain a form of tenofovir, though only two of the active products (oral TDF and oral FTC/TDF) are expected to have significant and consistent systemic absorption of tenofovir. The effects of tenofovir on BMD have been studied in animals and humans. Although clinically significant bone toxicity has not been observed in human trials of tenofovir performed to date, the effects of this drug on bone health in young, pre-menopausal women has not yet been studied and remains of potential concern.

Tenofovir and TDF administered orally in toxicology studies to rats, dogs, and monkeys at exposures (based on AUCs [areas under curves])  $\geq$  6-fold those observed in humans caused bone toxicity. In monkeys bone toxicity was diagnosed as osteomalacia. Osteomalacia observed in some monkeys appeared to be reversible upon dose reduction or discontinuation of tenofovir. In rats and dogs, bone toxicity manifested as reduced BMD. The mechanism(s) underlying bone toxicity is unknown. However, data in humans have been reassuring. Gilead Study 903, which continues to follow men and

women receiving tenofovir as part of an antiretroviral regimen, has reported on bone monitoring for up to six years in this cohort. Observed decreases in spine BMD were statistically significant at week 144 with a mean percentage decrease at the lumbar spine in patients receiving TDF + lamivudine + efavirenz (-2.2  $\pm$  3.9) compared with patients receiving stavudine + lamivudine + efavirenz (-1.0  $\pm$  4.6). Although observed decreases in spine and hip BMD were statistically significant, these percent changes from baseline are not clinically relevant, and no bone fractures related to TDF have been observed.

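### The primary BMD comparison is fixed as an unadjusted t-test; adjusting for baseline BMD, site and DMPA use, with month-6 scans in the model, would be a modest gain at almost no cost

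*Protocol*

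**What the plan says.** The primary test is named twice. Section 10.4 states: "Two Student t-tests (two-sided) will be used to compare the percentage reduction in BMD", using the mean of the duplicate scans at each time point. Section 10.5 repeats it for one year: "For the primary analysis, two Student t-tests will be used to compare the percentage reduction after one year of follow-up in BMD", with contrasts of TDF against placebo and FTC/TDF against placebo, hip and spine analysed separately. Neither section gives the primary test a covariate, a site term or a repeated-measures term. Baseline comparability of the arms is examined by descriptive statistics only.

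The same protocol collects what an adjusted analysis would need:

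- **Baseline BMD:** duplicate DXA at enrolment (sections 7.2.3 and 7.4).
- **Contraception history:** collected at enrolment (section 7.2.2). Section 2.2.1 treats DMPA as a possible modifier of BMD and expects that "approximately 48% of study participants used DMPA and a similar proportion might be expected in the VOICE Study".
- **Site:** section 7.4 plans a phantom exchange to check that scans from two sites are comparable, and section 10.4 says that measurement error at the sites is unknown.
- **Month-6 scans:** DXA is semiannual. Section 10.5 puts all time points into GEE models, but only to explore trends.

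**The concern.** The primary test leaves known prognostic information unused. A percentage change divides by baseline BMD but does not remove its remaining correlation with baseline, because measurement error and natural variation make high baseline values tend to fall and low ones tend to rise. Chance imbalance between arms in baseline BMD, site mix or DMPA use therefore passes into the estimate. The protocol offers only a descriptive look at it.

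A t-test on one-year change also has no way to use a woman who has a baseline and a month-6 scan but no month-12 scan. Section 7.6.1 suspends DXA during pregnancy, so some such women are to be expected, and the 100 per arm in section 10.4 carries no stated allowance for them.

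What is at stake is precision. The design is sized for 2.1%, while section 2.4 cites a loss of about 1% relative to placebo in two studies of men. At a true difference of 1% the planned test has power of only about 35%.

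**Working it through.** **Inputs.** All are from the protocol.

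- Sample size (section 10.4): "a minimum of 300 women will be enrolled in the study (i.e. 100 women per oral arm".
- SD of 12-month percentage change (section 10.4): "initiation of follow-up for the hip and lumbar spine is 4.5" per cent.
- Claim (section 10.4): the design "allows the detection of a difference as small as 2.1% with 90% power with a type one error rate of 5" per cent.
- Correlation of longitudinal BMD measurements (section 10.4): 0.85 to 0.95.
- Allocation (section 2.1): "randomized to the five study arms in a 1:1:1:1:1 ratio", hence equal among the three oral arms.

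**Step 1: reproduce the plan's figure.** Women per arm = 2 × (1.960 + 1.282)² × 4.5² / 2.1² = 96.5, so 97 against the planned 100. With 100 per arm, the detectable difference at 90% power is 4.5 × √(2/100) × (1.960 + 1.282) = 2.06% by the normal approximation, or 2.07% with the t distribution. Power at 2.1% is 90.7% (t distribution). The stated figure holds.

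**Step 2: add baseline BMD as a covariate.** With equal variance at both times, and treating percentage change as approximately a log-scale change, the residual variance relative to a change score is (1 + r)/2.

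| r | Variance ratio | Residual SD = 4.5 × √ratio | Detectable difference | Power at 2.1% | Equivalent women per arm = 100/ratio |
|---|---|---|---|---|---|
| none (t-test) | 1 | 4.50 | 2.07% | 90.7% | 100 |
| 0.85 | 0.925 | 4.33 | 1.99% | 92.7% | 108.1 |
| 0.90 | 0.950 | 4.39 | 2.02% | 92.1% | 105.3 |
| 0.95 | 0.975 | 4.44 | 2.05% | 91.4% | 102.6 |

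The gain is worth about 3 to 8 women per arm. At a true difference of 1%, power rises from 35% to 35–37%.

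**Step 3: DMPA (assumed effect).** If users and non-users differ by d points in annual change, the share of variance explained is 0.48 × 0.52 × d² / 4.5². For assumed d of 1, 2 and 3 this gives 1.2%, 4.9% and 11.1%. The protocol supplies no d.

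Chance imbalance can be sized in the same way. The standard error of the between-arm difference in DMPA share is √(2 × 0.48 × 0.52 / 100) = 0.071. A two-standard-error imbalance with an assumed d of 2 would move the estimate by 2 × 0.071 × 2 = 0.28 points.

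**Step 4: missing month-12 scans (assumed rates).** With 10% or 20% missing, 90 or 80 women per arm remain and t-test power at 2.1% is 87.6% or 83.5%.

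For a likelihood-based model, the variance is proportional to (1 − ρ²)/n₁₂ + ρ²/n₆. Here ρ is the correlation between the month-6 and month-12 changes, n₁₂ is the number with a month-12 scan, and n₆ is the number with a month-6 scan. Assume ρ of 0.5 to 0.7, and that half to all of the women with a missing month-12 scan have a month-6 scan. By the normal approximation, power moves from 87.9% to 88.3–89.4% at 10% missing, and from 83.9% to 84.9–87.5% at 20% missing.

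**The case against.** The strongest reply is that nothing here is wrong. The arms are randomised and blinded within the oral mode, so an unadjusted comparison of complete scans is unbiased, and the power statement matches the test. That stands.

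The title of section 10.5's test might also lead a reader to infer more than the documents support:

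- **That baseline and month-6 data are thrown away.** They are not. Baseline BMD is the denominator of every percentage change, and month-6 scans enter the GEE. Only their use in the primary estimate is absent.
- **That every woman without a month-12 scan is dropped.** This is a fair inference from the test, but the protocol states no analysis set, visit window or missing-data rule, and these may be in an analysis plan that is not shown. Scans are also taken at the PUEV or early termination visit if at least 30 days after the last semiannual visit, and may resume after pregnancy.
- **That DMPA adjustment would bring a large gain.** Section 2.2.1 itself describes the effects of DMPA and breastfeeding as probably small and reversible, which argues against the upper end of the range in step 3. No figure for site can be derived at all.
- **That the design must detect 1%.** That figure is background from men. The sample size is set for 2.1%.
- **That the two active arms ought to be pooled.** Section 2.2.2 notes that "only two of the active products (oral TDF and oral FTC/TDF) are expected to have significant and consistent systemic absorption of tenofovir", which makes pooling tempting. But the objective and section 10.5 call for two separate contrasts, and a pooled one answers a different question.

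It is also true that the sizeable gain is small beside the recruitment range of 300 to 540. With 180 per arm, the same t-test detects about 1.54%.

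What does not stand is that the matter can wait for an analysis plan. The protocol names the primary test twice, so an adjusted primary analysis would have to depart from it.

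**Conclusion.** The point holds as an efficiency improvement. The t-test is valid and its power figure is right, but it makes less use of the collected data than it could.

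The only gain that can be sized from the document is the one from baseline BMD: 2.5% to 7.5% of variance, a detectable difference of 1.99% to 2.05% instead of 2.07%, and power at 2.1% of 91.4% to 92.7% instead of 90.7%. This rests on the protocol's SD of 4.5%, its correlations of 0.85 to 0.95, and equal variances at the two times. The figures for DMPA and for missing scans rest on assumed effects and rates. They show what adjustment and month-6 data could protect against, not what they will deliver.

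**What to change.** In sections 10.4 and 10.5, keep the endpoints, the separate hip and spine analyses, and the two month-12 active-versus-placebo contrasts. Replace the primary t-tests with a baseline-adjusted model:

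- **Preferred:** for each skeletal site, a likelihood-based repeated-measures model of percentage change at months 6 and 12 in all three arms. Its terms are arm by visit, baseline BMD (mean of the duplicates) by visit, study site and baseline DMPA use.
- **Minimum:** ANCOVA of month-12 percentage change on arm, baseline BMD, study site and baseline DMPA use.

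Name the covariates before unblinding, since covariates chosen afterwards carry less weight. Keep the t-tests as a sensitivity analysis. The sample size statement can remain, described as not counting the gain from adjustment. A pooled contrast of the two tenofovir-containing arms is optional and not part of this correction.

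The cost is analysis wording and a slightly longer model specification. No new data, visits or participants are needed. The repeated-measures model treats missing scans as missing at random given the observed data, and that assumption should be stated.

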## Secondary Objectives:

- To describe changes over time in nutritional assessment components among VOICE participants receiving oral study products.
- To compare changes in BMD over the duration of the BMD Substudy among participants receiving oral TDF and FTC/TDF compared with placebo.
- To evaluate changes in BMD in the 12 months following the discontinuation of an oral study product in VOICE.

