#### 4.6 Expected Duration of Participation

The expected duration of participation in the BMD Substudy is approximately 48 months total. Accrual will require approximately 21 months. Follow-up will continue for 12 months after the VOICE PUEV.

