## 7.3 Follow-up Visits

Follow-up visits will occur on a semiannual basis (approximately every 6 months) and may be completed on the same day as VOICE Study visits. The follow-up visits will occur at 6 months and 12 months following the VOICE PUEV. The semiannual follow-up visit procedures listed below will also be completed at either the VOICE PUEV or the BMD Substudy ETV if at least 30 days have passed since the last semiannual follow-up visit.

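### The exploratory GEE over all time points mixes on-product and post-PUEV scans, which flattens a longer-term on-product BMD trend towards no effect

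*Protocol*

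**What the plan says.** Protocol section 10.5 compares each active arm with placebo by t-test at one year. It then notes that many women will leave VOICE before their year-2 scan: "Assuming uniform recruitment over 21 months, about 130 of the 300 women will have a year-2 BMD assessment". Its response to the smaller number is a repeated-measures model "to explore possible trends over the entire follow-up time", described as follows: "GEE models for repeated measures will be used where BMD from all time points are included in the analysis".

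The secondary objective that this model serves, in section 3, is "To compare changes in BMD over the duration of the BMD Substudy among participants receiving oral TDF and FTC/TDF compared with placebo".

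The substudy does not end with product use. Section 4.6 says "Follow-up will continue for 12 months after the VOICE PUEV", section 7.3 says "The follow-up visits will occur at 6 months and 12 months following the VOICE PUEV", and Table 1 lists DXA among the procedures at those visits. The length of the product period differs between women; section 2.1 says of VOICE that "All participants will complete monthly follow-up visits for a period of 12 to 36 months".

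A later paragraph of section 10.5 plans separate t-tests of the change over the year without product.

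**The concern.** Women reach PUEV at different times since enrolment. At a given month after month 12, early enrollees are still taking product while late enrollees have stopped and may be regaining bone. A model indexed by time since enrolment, with no product-use term, counts off-product months as exposure and averages any loss with any recovery.

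The GEE is the only named analysis of on-product BMD change beyond one year. Sections 2.3 and 10.3 hypothesise no clinically significant decrease, so a trend pulled towards zero favours the hypothesis. Section 2.4 itself raises the possibility that tenofovir-related loss reverses after stopping.

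The year-2 count in the same paragraph also sits badly with the visit schedule. It reads as if the remaining women had no scan near year 2, yet they are then in their off-product year and still being scanned.

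**Working it through.** **Inputs from the protocol.** 300 women, the planning minimum (10.4); uniform accrual over 21 months (10.5); minimum VOICE follow-up of 12 months (2.1); scans every 6 months, at PUEV if at least 30 days after the last scan, and at PUEV+6 and PUEV+12 (4.1, 7.3, Table 1).

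**Assumptions.** PUEV is uniform over 12 to 12+21 = 33 months; 30 days is taken as one month; there is no dropout, product hold or early discontinuation; recovery over the 12 off-product months is linear and equals 0%, 50% or 100%. The protocol gives no recovery figure.

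**1. The plan's own count.** Still on product at month 24: (33-24)/21 × 300 = 9/21 × 300 = 128.6. This reproduces about 130, but only as women still in VOICE. The other 300 - 128.6 = 171.4 are between 0 and 12 months past PUEV, 6 months on average.

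**2. Women by product status.**

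| Month since enrolment | Still followed | On product | Off product | Share off |
|---|---|---|---|---|
| 18 | 300 | 214 | 86 | 29% |
| 24 | 300 | 129 | 171 | 57% |
| 30 | 214 | 43 | 171 | 80% |
| 36 | 129 | 0 | 129 | 100% |

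**3. Scans by product status, per woman.**
- On-product: months 6 and 12 (2), months 18, 24 and 30 (15/21 + 9/21 + 3/21 = 27/21), and a separate PUEV scan (17/21, since 4 of the 21 months fall within a month of a semiannual scan). Total 2 + 44/21 = 4.10.
- Off-product: 2.
- Off-product share overall: 2/6.10 = 33%.
- From month 24 onward: on-product 9/21 + 3/21 + 7/21 = 19/21; off-product 15/21 + 21/21 = 36/21; share off 36/55 = 65%.
- In the window from month 21 to month 27 alone: on-product 14/21, off-product 9/21; share off 9/23 = 39%. Off-product scans are timed from PUEV, so they do not all fall at month 24.

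**4. Plateau effect at month 24.** Off-product women average 6 of 12 months past PUEV.
- Full recovery: 0.43 × 1 + 0.57 × 0.50 = 0.71 kept.
- Half recovery: 0.43 × 1 + 0.57 × 0.75 = 0.86 kept.
- No recovery: 1.00 kept.

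**5. Linear arm-by-time slope.** The expected difference from placebo at month t, for a woman with PUEV at P and s months since PUEV, is -1.0 × min(t, P)/12 × (1 - r × s/12), with r the recovered fraction. Fitting this without noise to the visit schedule gives, in % per year:

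| Model | r = 0 | r = 0.5 | r = 1 |
|---|---|---|---|
| Independence, no arm intercept | -0.82 | -0.65 | -0.48 |
| Exchangeable 0.85, no arm intercept, baseline included | -0.73 | -0.46 | -0.19 |
| Exchangeable 0.5, arm intercept, baseline included | -0.72 | -0.45 | -0.18 |
| Exchangeable 0.9, arm intercept, baseline included | -0.72 | -0.45 | -0.17 |
| Any of these, scans through PUEV only | -1.00 | -1.00 | -1.00 |

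Correlations of 0.85 to 0.95 are those that section 10.4 gives for repeated BMD measurements. Flattening occurs even with r = 0, because off-product months still count as time.

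**The case against.** The strongest case is that the author meant on-product scans. The count of about 130 works only for women still in VOICE, the GEE is introduced as the answer to that attrition, section 10.4 ties the primary analysis to the product-use period, and the off-product year has its own paragraph and tests. On that reading nothing is diluted. The reading is possible, but the words set no such limit, and the matching objective covers the whole substudy. An SAP that restricted the set would depart from the protocol text.

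A second argument is that an all-scan comparison answers the stated objective: the on/off mix should be similar across randomised arms, so it is not confounded by arm. That is true of an average over the substudy. It does not make a slope against time since enrolment a measure of continued product use.

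A third is that the protocol fixes no time axis, model terms or working correlation, and that recovery is assumed. This stands, and is why ranges are given. The slope alone also understates what such a model would show: with an arm intercept, correlation 0.5 and full recovery, the intercept is about -0.59%, so an arm difference remains visible. Other choices fall outside the range: with an arm intercept, correlation 0.9 and no baseline row, the full-recovery slope is about +0.08.

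A reader might infer that the effect is erased, or that this is the only planned analysis of BMD beyond one year. Neither is supported. At least 71% of a plateau effect remains at month 24, near-loss of a plateau effect (13% left) arises only around month 42 under full recovery, when nobody is on product, and section 10.5 analyses the off-product year separately.

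**Conclusion.** The point holds for the text as written. The exploratory GEE includes off-product scans without distinguishing them: about a third of post-baseline scans, and about 65% of those from month 24 onward. A linear on-product trend of -1.0% per year would be reported at between roughly four fifths of its size (no recovery) and between one sixth and one half of it (full recovery). Visit-wise contrasts lose 0 to 29% at month 24.

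These sizes rest on uniform accrual, no dropout, linear recovery and the model forms shown. Section 2.4 says that reversibility has not been studied in HIV-uninfected people, so no single figure can be called the expected bias. It would also be wrong to infer that the main result is at risk: the one-year t-tests fall within the 12-month minimum product period, and the off-product t-tests are unaffected. Severity is moderate, because the analysis is exploratory and secondary.

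**What to change.** In section 10.5, do one of the following:
- fit the on-product GEE to scans up to and including PUEV; or
- fit one model to all scans with separate arm-by-time-on-product and arm-by-time-since-PUEV terms, and report both effects.

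If an average over the whole substudy is also wanted for the secondary objective, keep it as a separately labelled result.

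Relabel the figure of about 130 of 300 as women expected to have an on-product year-2 scan before losses, and add that the remaining 170 or so are scanned off product around that time.

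The cost is a wording change in the protocol, carried into the SAP. It needs no extra visits or data.
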